Randomization will be performed at the patient level using computer-generated assignment. Eligible patients who provided written informed consent will be randomized to receive the intraoperative electroencephalography-guided protocol or routine care. In order to ensure that there is not major imbalance between group assignments with respect to history of falls and cardiac surgery, subjects will be randomized (1:1) between the EEG-guided and routine care groups in blocks of 20 within these four strata (i.e., cardiac surgery with a history of falls within 6 months, cardiac surgery without a history of falls within 6 months, non-cardiac surgery with a history of falls within 6 months; and non-cardiac surgery without a history of falls within 6 months). Trained members of the research team will enroll participants and will implement the assignment of participants to the EEG-guided or usual care protocols. Group assignment will be revealed to members of the anesthetic team only when the patient enters the operating room by opening a sequentially numbered, opaque, sealed envelope in a sequence generated by one of the study's data analysts. Patients and their families will be blinded to group allocation and different members of the research team will assist with the intervention in the operating room (will not be blinded to the intervention) from those conducting the postoperative assessments (will be blinded to the intervention).^{51,52} To reduce predictability of a random sequence, details of patients already randomized and prior group assignments will be recorded in a separate document that is unavailable to those who enroll participants and assign interventions.

Primary Intervention – EEG-guided Anesthetic Protocol

The primary intervention to which patients will be randomized in this study is a pragmatic EEG-guided anesthetic protocol (See Appendix). All anesthesia practitioners will receive a targeted educational session on recognition of EEG patterns typically occurring during general anesthesia. The content will be similar to that described in an article where we demonstrated that anesthesiologists could estimate BIS (processed EEG

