Patients who are unable to speak (e.g., have a tracheal tube or tracheostomy) will instead be assessed using the Confusion Assessment Method for the Intensive Care Unit (CAM-ICU) instrument.^{89,90} Both of these methods (the CAM and the CAM-ICU) have been shown to be reliable and to have good agreement with the DSM-IV criteria for delirium.⁹⁰⁻⁹² In addition to the CAM or the CAM-ICU, an independent trained clinical researcher, blinded to the CAM results, will conduct structured chart reviews to detect episodes of delirium. A combined approach (CAM interview or CAM-ICU plus chart review) increases the sensitivity and retains specificity in detecting incident delirium.^{93,94} Therefore, either a positive clinical delirium assessment (CAM or CAM-ICU) or a positive assessment for delirium based on a validated, structured chart review^{93,94} will be diagnostic of incident delirium in the ENGAGES trial. The use of the structured chart review will both improve sensitive and contribute to the pragmatic aspects of this trial, since it will abstract incident delirium from a routinely available source. The trial staff will undergo training on the chart review methodology by a skilled chart reviewer under the supervision of Drs. [name] and [name].

The CAM assessment that will be used in the ENGAGES study was developed by [name] and colleagues.²¹ All ENGAGES CAM assessments will be performed by study team members who have undergone a rigorous training process. Several members of the research team participated in a full-day CAM training program led by [name], the original creator of the instrument.⁹⁵ Those who attended this initial training will oversee the training of other team members. All trainees must demonstrate competence at conducting the structured

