We will follow the intention-to-treat principle for all analyses. The primary endpoint of our analysis is the incidence of postoperative delirium as defined previously. The incidence of delirium will be compared between groups using a chi-square test, and the difference in delirium incidence with 95% confidence intervals will be calculated. Prespecified exploratory subgroup analyses: we will test for effect modification by known baseline delirium risk factors (i.e., age [<70 and ≥ 70], sex, history of falls, and type of surgery [cardiac versus non-cardiac]).

ii) Effectiveness of EEG-guided anesthesia protocol in improving patient reported outcomes of health-related quality of life and preventing postoperative falls (Aim 2 in Figure 2)

Health-related quality of life

Random effects regression models based on PROC MIXED in SAS will be used to compare Physical Summary Score change over 12 months between the intervention and usual care group by introducing terms for time, indicator variables for treatment group and time x treatment group interactions with the latter set of regression coefficients of primary interest. The model will be controlled for baseline health-related quality of life. Potential confounding factors including age, gender and relevant comorbidities will be evaluated and controlled for in the model. We will utilize the same analysis approach to evaluate the Mental Summary Scores.

The analysis is primarily based on the following model: $Y_{it} = \alpha + \beta_1 t + \beta_{2A} X_{i1} + \beta_{3A} X_{i1}t + \beta_4 Y_{i0} + e_{it}$ (1) where Y_{it} = QOL for subject i at time t , where $t = 0$ for baseline, $t = 1$ for 12 months. $X_{i1} = 1$ if i th subject is in the Intervention group, = 0 otherwise $e_{it} \sim N(0, \sigma^2)$ β_{3A} is the mean difference in Physical Summary Score change between the Intervention and usual care groups. The coefficient β_{2A} allows for mean differences in Physical Summary Scores between groups at baseline. The coefficient β_4 allows the change in Physical Summary Score to depend on initial level.

Postoperative falls

Chi square test will be used to compare the incidence of falls at 12-months postoperatively between patients in the EEG-guided and in the usual care groups.

iii) Explore whether a multi-component safety intervention is associated with improved patient reported health-related quality of life and decreased incidence of postoperative falls (Aim 3 in Figure 2)

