According to seven of nine criteria elaborated in the pragmatic-explanatory continuum indicator summary (PRECIS-2) tool¹¹¹, the ENGAGES trial is designed predominantly as a pragmatic rather than as an

during the first phase of the study, there will be structured education of clinicians to increase their familiarity and comfort with EEG-guidance of anesthesia. We therefore anticipate that practitioner familiarity with EEG will increase over the course of the study, although only basic knowledge regarding EEG analysis will be needed. Similarly, any anesthesia practitioner, regardless of their background or expertise, can apply the control (comparison) protocol. 5) Instructions on how to apply the EEG-guided protocol are flexible, offering practitioners discretion in deciding how to formulate and apply it. Although clinicians carrying out the EEG-guided protocol will use their own discretion in managing anesthesia, there is an expectation that less anesthesia will be administered in the EEG-guided arm and that the cumulative duration of EEG suppression will be less in the EEG-guided arm. During the first phase of the study, clinician adherence to the EEG-guided protocol will be evaluated and will partially inform the value of proceeding with the second phase of the study. Similar to the intervention arm, when patients are randomized to the control arm, anesthesia clinicians will have leeway to pursue their usual practice with minimal restrictions. There are some limitations in relation to anesthetic technique (e.g. based on potent volatile anesthetic), however these are consistent with current practice at our institution and more broadly. 6) For the primary intervention of the ENGAGES trial, participants will be anesthetized and will have no ability to impact adherence to the intervention. Therefore, this domain was left blank in the PRECIS-2 determination, as recommended¹¹¹. 7) Patients enrolled to the ENGAGES trial will be followed with more frequent visits and more extensive data collection than would occur in routine practice. 8) Incident delirium, the primary outcome of the study, is an objectively measured, clinically meaningful outcome to the study participants. The outcome can be assessed under usual conditions and typically does not rely on central adjudication. However, special training in rigorous delirium assessment is required. It is important to note that the abstraction of information of delirium from the medical records bolsters the pragmatic aspects of the trial, since this is an information source that is readily available at any hospital. 9) The analysis of the results will include all patients regardless of clinician compliance with the EEG-guided protocol (i.e. it will be an “intention-to-treat” analysis). The analysis will attempt to determine whether or not the EEG-guided protocol prevents postoperative delirium under the usual conditions, with all the noise inherent therein. Although in most respects the ENGAGES trial was judged to be pragmatic, this appraisal might have been biased as it was conducted by investigators associated with the study.¹¹²

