The following limitations should be considered. A single clinical trial should seldom be regarded as definitive. As there is no clear estimate for the prior probability that EEG guidance of anesthesia prevents postoperative delirium, if the results of this trial do suggest that EEG-guidance of anesthesia might decrease delirium at the arbitrary statistical threshold of $p < 0.05$, it will be necessary to replicate this finding in future studies. On the other hand, even if the study finds a non-significant (at the arbitrary threshold of $p > 0.05$) decrease in delirium in the EEG-guided group, it is likely that follow-up studies will be warranted to clarify whether or not there is a clinically meaningful reduction in delirium with EEG-guidance of anesthesia, and whether there are specific patient populations that might especially benefit from this intervention. If EEG-guidance of anesthesia can prevent postoperative delirium, demonstrating its effectiveness will depend on clinicians' adherence to the protocol. However, the inability to blind clinicians to the trial allocation group is a potential source of bias and confounding. We are attempting to confirm that clinicians do alter anesthetic management based on the intervention during the pilot phase of the study. The inclusion of patients in a clinical trial focused on the prevention of delirium, and the provision of practical educational information to patients and family members could decrease the incidence of postoperative delirium. Furthermore, if the multi-component intervention is successful in preventing falls and in improving quality of life, this could curtail our ability to detect an impact of the EEG-guided anesthetic protocol on these outcomes. In addition to the pragmatic structured chart review, there are two clinical assessment methods that will be used to diagnose delirium: the CAM-ICU and the CAM. The CAM-ICU is less sensitive than the CAM, but is the only instrument that has been validated for patients who are non-verbal (i.e., with a breathing tube or tracheostomy in place). Based on our institutional data, the vast majority of patients enrolled in the study will be extubated within the first two postoperative days. Therefore, most patients will have delirium assessments with the CAM, which is the more sensitive and specific instrument. We will also test whether intubation status modifies the result in secondary analysis. The study design includes a 30-day and a 1-year follow up for patient reported outcomes, and incomplete follow-up is therefore a potential limitation. Based on our previous B-Unaware and BAG-RECALL studies,^{40,41} we are confident that we can achieve a 30-day follow up rate of >90%. In our SATISFY-SOS cohort, the 1-year follow up has yielded approximately 66% response rate. We have performed sensitivity analysis in our power calculations and have taken into account this potential attrition in our methods. Furthermore, we plan to enhance follow-up by using supplementary phone calls from members of the study team. As delirium is a fluctuating disorder, there is a risk that it can be missed by periodic assessments. We are attempting to mitigate this by assessing patients for delirium during a time of day (afternoon/evening) when delirium occurs more commonly. Furthermore, we are incorporating structured chart review, which has been validated as a complementary approach that increases the detection of delirium.^{93,94}

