Delirium incidence, duration and severity have all been shown to be associated with other (downstream) clinically relevant outcomes, including mortality, length of ICU stay, length of hospital stay, falls, cognitive decline and functional decline. In the ENGAGES study, these associations will be explored. The data on downstream outcomes will be obtained from hospital records or from patient reported outcomes measures that are collected as part of the ongoing SATISFY-SOS study.

e) Comparison of patient-reported and observational pain scores

It is likely that patients with delirium are less able to convey verbally the extent to which they are in pain.¹³⁰ Given that postoperative delirium is common and may relate to uncontrolled pain, this has important implications for the assessment and treatment of postoperative pain. We plan to compare patient reported and behavioral pain assessments in both non-delirious and delirious patients.¹³⁰ (See Appendices for pain assessment instruments)

(conducted with the CAM-ICU) will be collected when these are available. Comparison will be made between these routine clinical assessments and the assessments made by the research team.

h) Association Between Delirium and Patient Outcomes

The ENGAGES study will evaluate the association between postoperative delirium and patient reported outcome metrics, including quality of life and falls, up to one year postoperatively.

i) Postoperative outcomes hypothesized to be associated with anesthetic depth

It is likely that patients randomized to the EEG-guided protocol will be exposed to lower concentrations of anesthetic agents, and on average will not be as deeply anesthetized. There is an ongoing randomized, clinical trial investigating the effects of depth of anesthesia on a range of outcomes^{101,102}, including death, myocardial infarction, cardiac arrest, pulmonary embolus, stroke, surgical site infection, ICU length of stay, hospital length of stay, intraoperative awareness, persistent pain and cancer recurrence. Many of these outcomes are tracked with the SATISFY-SOS study, and will therefore be reported for patients enrolled in the ENGAGES study.

j) Delirium Prediction Models

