It is important to improve our understanding of factors that are associated with an increased incidence of postoperative delirium or perhaps may even mediate an elevated risk for postoperative delirium. Previous studies have explored risk factors, usually using logistic regression models.^{29,136-148} In a previous study we used a Bayesian exploratory approach with a stochastic search variable selection method.²⁹ The ENGAGES study will rigorously assess a large number of surgical patients for postoperative delirium, and it will therefore lend itself to further exploration, refinement of risk models and hypothesis generation. Based on results from previous studies, we will include specific variables in our analyses. Patient age, demographic, life style and comorbidity information will be assessed at baseline through a standardized interview in the CPAP clinic. Data on previously described risk factors for postoperative delirium will be acquired including: history of postoperative delirium, modified Charlson Comorbidity Index, American Society of Anesthesiologists' Physical Status, functional status, level of education, olfaction, baseline cognition, depression (using the PHQ-9 questionnaire), indices of frailty, obstructive sleep apnea, baseline hematocrit, baseline sodium and creatinine, preoperative psychoactive medications (e.g. opioids, benzodiazepines, sedatives, clonidine), alcohol use, dosages of perioperative medications (e.g. hypnotic anesthetics, opioids, benzodiazepines, dexmedetomidine), intraoperative hemodynamic parameters, other physiological parameters, processed EEG indices (e.g. BIS, burst suppression), vasoactive medications, perioperative blood transfusions, postoperative mechanical ventilation, postoperative pain (using visual analogue scale and behavioral pain scale), postoperative sleep deprivation, postoperative medical complications, postoperative shock, postoperative anemia (hematocrit <30%), postoperative hypoalbuminemia (albumin <3 g/dL), postoperative temperature, and postoperative sodium concentration.^{29,79,136-148}

Collaborations with Other Studies

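### Intubation status arises after randomisation, so delirium comparisons within intubated or extubated patients are not randomised and cannot isolate CAM-ICU sensitivity

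*Combined protocol and SAP*

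**What the plan says.** The sentence at issue is in the protocol's Strengths and Limitations section, in the discussion of CAM versus CAM-ICU: "We will also test whether intubation status modifies the result in secondary analysis". Shortly before it, the text says: "Based on our institutional data, the vast majority of patients enrolled in the study will be extubated within the first two postoperative days". The status meant is therefore intubation after surgery. The motive is stated too: the CAM-ICU is the less sensitive instrument. Outcome Measures i) ties instrument to status, with the CAM-ICU replacing the CAM: "Patients who are unable to speak (e.g., have a tracheal tube or tracheostomy) will instead be assessed using the Confusion Assessment Method for the Intensive".

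Four other places bear on the point:

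- Randomization and Blinding: "Group assignment will be revealed to members of the anesthetic team only when the patient enters the operating room". Allocation thus precedes the anaesthetic and any postoperative intubation.
- Analysis of Pragmatic Elements: "there is an expectation that less anesthesia will be administered in the EEG-guided arm". Sub-study i) in the addendum adds that EEG-arm patients "on average will not be as deeply anesthetized".
- Sub-study j), Delirium Prediction Models, includes "postoperative mechanical ventilation" among previously described risk factors.
- Statistical Analyses i): "we will test for effect modification by known baseline delirium risk factors", naming age, sex, falls history and type of surgery.

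The available text gives no time point, model or scale for the intubation analysis. Text is missing around the analysis sections, so I do not count that as an omission. The one-year SAP does not cover delirium.

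**The concern.** A subgroup comparison keeps the protection of randomisation only if the subgroup is fixed before treatment or cannot be changed by it. Postoperative intubation is not fixed before treatment, and a lighter anaesthetic might plausibly change it. If it does, the intubated patients in one arm are a different selection from those in the other, and likewise the extubated patients. If severity also drives delirium, the arms then differ within each stratum even when EEG guidance does nothing.

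There is a second problem that does not depend on any arm effect. Intubated patients differ from the rest both in the instrument used and in their underlying risk. If the treatment effect did appear to differ by intubation status, the analysis could not say whether the CAM-ICU or the type of patient was responsible, and the instrument question was the reason for doing it.

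At stake is the reading of one secondary analysis: a stratum result could be taken as a real benefit or harm, or as proof that the instrument distorted the primary result.

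**Working it through.** **1. The plan's own figure.** The inputs reproduce. With 616 per arm, 25% control incidence, two-sided 0.05 and the pooled-variance normal approximation, power = Φ[(d − 1.96·SE₀)/SE₁]. For d = 0.07, the mean proportion is 0.215:

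- SE₀ = √(2·0.215·0.785/616) = 0.02341
- SE₁ = √((0.25·0.75 + 0.18·0.82)/616) = 0.02332
- power = Φ[(0.07 − 0.0459)/0.0233] = 85.0%

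For 8 and 9 points the results are 93.2% and 97.5%. All three stated bounds (80%, 90%, 95%) hold. This only confirms the inputs; the concern is structural.

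**2. A model with no treatment effect on delirium.** From the documents: 616 per arm and 25% delirium, applied to both arms. Assumed: an unmeasured severity S ~ N(0,1); logit P(delirium) = a + bS with b = 0.5 or 1.0 (a = −1.158 or −1.315 gives 25%); a patient is intubated when (S + noise)/√2 exceeds the normal quantile for that arm's intubated share. The shares are assumptions. Instrument error is not modelled.

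Delirium risk among the intubated is ∫D(s)π(s)φ(s)ds / ∫π(s)φ(s)ds, where D is delirium risk, π is intubation probability and φ is the normal density. For the extubated, 1 − π replaces π. The last three columns are rejection rates at two-sided 0.05 in 20,000 simulated trials (Wald tests on log odds ratios).

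| Intubated, control vs EEG | b | Difference, intubated | Difference, extubated | False positive, intubated | False positive, extubated | Interaction |
|---|---|---|---|---|---|---|
| 20% vs 20% | 0.5 / 1.0 | 0 / 0 | 0 / 0 | 5% / 5% | 5% / 5% | 5% / 5% |
| 20% vs 15% | 0.5 / 1.0 | +1.2 / +2.4 | +0.5 / +0.9 | 5% / 6% | 6% / 6% | 5% / 5% |
| 20% vs 10% | 0.5 / 1.0 | +2.8 / +5.5 | +1.0 / +1.9 | 7% / 11% | 7% / 11% | 5% / 6% |

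Differences are EEG minus control, in percentage points. Repeat simulations of the 20% vs 10% case agree within simulation error (+2.6 to +5.5 points in the intubated; stratum false positives 6% to 12%).

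Check for 20% vs 10%, b = 1.0:

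- Control: 0.2·0.4283 + 0.8·0.2054 = 0.250.
- EEG: 0.1·0.4832 + 0.9·0.2241 = 0.250.

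Both strata show apparent harm although the arms are identical overall.

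**3. Sampling error.** In that case about 0.2·616 = 123 and 0.1·616 = 62 intubated patients are compared. SE = √(0.4283·0.5717/123.2 + 0.4832·0.5168/61.6) = 7.8 points, larger than the 5.5-point bias. At b = 0.5 it is 7.5 points against 2.8.

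**4. Other assumptions.** A second model makes both intubation and delirium logistic in severity:

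- Shares 30% vs 20%, severity unrelated to intubation: odds ratios 1.00, no bias.
- 30% vs 20%, both slopes 1: false odds ratios 1.09 (intubated) and 1.08 (extubated); stratum false positives 7% to 8%; interaction 5%.
- 30% vs 15%, both slopes 2: odds ratios 1.49 and 1.37; stratum false positives 34% and 43%; interaction 6%.
- 30% vs 20%, severity–intubation slope 1 in control and 2 in EEG, delirium slope 1: odds ratios 1.46 and 0.97; interaction rejected in 30%.
- The same with slopes 0.5 and 2: interaction rejected in 71%. With equal shares of 20% it is still 65%.

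Shifting only the share intubated produces false stratum effects with a near-nominal interaction test. Frequent false interactions require the arm to change which patients stay intubated.

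**The case against.** The strongest reply is that the planned analysis is a test of modification, and under a plain shift in the share intubated that test holds close to its nominal level. A reader might infer from the structural argument that the plan will readily produce false interactions. The calculations do not support that without arm-specific selection into intubation, and no part of the documents gives a basis for the slopes that produce it.

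Second, the documents nowhere say that EEG guidance alters time to extubation. The protocol's Background even notes that trials have led practitioners to doubt whether it meaningfully changes anaesthetic administration. The 20% versus 10% split is an illustration. This stands, and it limits any claim about size.

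Third, a reader might see a contradiction between the baseline modifiers in Statistical Analyses i) and the intubation sentence. That section does not call its list exclusive, and the intubation test is separately labelled secondary, so there is a contrast but no breach.

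Fourth, delirium also counts as present when the blinded structured chart review is positive, which eases the CAM-ICU concern, and the protocol discloses that concern openly. This stands too, but it lessens the need for the test and does not make it valid.

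Finally, it is tempting to set the stratum bias against the 3% decrease that the sample size section calls clinically important. That figure concerns the whole trial, and the intubated-stratum differences carry standard errors of 7.5 to 7.8 points.

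What survives is the principle: strata defined after allocation are not randomised comparisons, and they mix instrument with patient risk.

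**Conclusion.** The concern holds as a minor point. Bias within strata needs two links: the arm must change intubation, and intubation and delirium must share causes. The documents make the second plausible, and the first only by inference from lower anaesthetic exposure. If the arm changes neither the share intubated nor which patients remain intubated, this bias is zero. The inability to separate instrument from selection remains in either case.

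The stratum false-positive rates of about 6% to 12% belong to the 20% versus 10% illustration. They would be higher only under stronger assumed selection.

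The primary chi-square comparison of all randomised patients does not condition on intubation and is unaffected. Confidence is high on the principle and low to medium on material impact.

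**What to change.** Do not treat intubation status as a formal effect modifier. In its place:

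1. Report by arm the number of delirium assessments done by CAM, done by CAM-ICU and not assessable. This addresses the instrument question more directly and shows whether use of the CAM-ICU differed by arm. Similar counts would not prove the strata comparable, since the arm could change who stays intubated without changing how many.
2. Present delirium by intubation status, at a defined time point, as descriptive and non-causal, without an interaction test.
3. For formal effect modification, rely on cardiac versus non-cardiac surgery. It is fixed before allocation, is a randomisation stratum and is already a prespecified modifier. State that it does not isolate instrument sensitivity.

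The cost is one changed sentence and one descriptive table from data already collected. The downside is losing the formal test by actual intubation status.
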